4.5 Rescue/Supportive Care Medications & Lifestyle Guidelines

Subjects should receive appropriate supportive care measures as deemed necessary by the treating investigator. Suggested supportive care measures for the management of adverse events with potential immunologic etiology are outlined below. Where appropriate, these guidelines include the use of oral or intravenous treatment with corticosteroids as well as additional anti-inflammatory agents if symptoms do not improve with administration of corticosteroids. Note that several courses of steroid tapering may be necessary as symptoms may worsen when the steroid dose is decreased. For each disorder, attempts should be made to rule out other causes such as metastatic disease or bacterial or viral infection, which might require additional supportive care. The treatment guidelines are intended to be applied when the investigator determines the events to be related to pembrolizumab. Note: if after the evaluation the event is determined not to be related, the investigator does not need to follow the treatment guidance (as outlined below). Refer to Section 4.4 for dose modification.

It may be necessary to perform conditional procedures such as bronchoscopy, endoscopy, or skin photography as part of evaluation of the event.

Pneumonitis:

- For Grade 2 events, treat with systemic corticosteroids. When symptoms improve
 to Grade 1 or less, steroid taper should be started and continued over no less than
 4 weeks.
- For **Grade 3-4 events**, immediately treat with intravenous steroids. Administer additional anti-inflammatory measures, as needed.
- Add prophylactic antibiotics for opportunistic infections in the case of prolonged steroid administration.

Diarrhea/Colitis:

Subjects should be carefully monitored for signs and symptoms of enterocolitis (such as diarrhea, abdominal pain, blood or mucus in stool, with or without fever) and of bowel perforation (such as peritoneal signs and ileus).

 All subjects who experience diarrhea/colitis should be advised to drink liberal quantities of clear fluids. If sufficient oral fluid intake is not feasible, fluid and

Initial Version date: March 10th, 2017

Amandment 6: March 20th, 2010

Amendment 6: March 29th, 2019

electrolytes should be substituted via IV infusion. For Grade 2 or higher diarrhea, consider GI consultation and endoscopy to confirm or rule out colitis.

- For Grade 2 diarrhea/colitis, administer oral corticosteroids.
- For Grade 3 or 4 diarrhea/colitis, treat with intravenous steroids followed by high dose oral steroids.
- When symptoms improve to Grade 1 or less, steroid taper should be started and continued over no less than 4 weeks.

Type 1 diabetes mellitus (if new onset, including diabetic ketoacidosis [DKA]) or ≥ Grade 3 Hyperglycemia, if associated with ketosis (ketonuria) or metabolic acidosis (DKA)

- For T1DM or Grade 3-4 Hyperglycemia
 - Insulin replacement therapy is recommended for Type I diabetes mellitus and for Grade 3-4 hyperglycemia associated with metabolic acidosis or ketonuria.
 - Evaluate patients with serum glucose and a metabolic panel, urine ketones, glycosylated hemoglobin, and C-peptide.

Hypophysitis:

- For Grade 2 events, treat with corticosteroids. When symptoms improve to Grade 1 or less, steroid taper should be started and continued over no less than 4 weeks. Replacement of appropriate hormones may be required as the steroid dose is tapered.
- For **Grade 3-4** events, treat with an initial dose of IV corticosteroids followed by oral corticosteroids. When symptoms improve to Grade 1 or less, steroid taper should be started and continued over no less than 4 weeks. Replacement of appropriate hormones may be required as the steroid dose is tapered.

Hyperthyroidism or Hypothyroidism:

Thyroid disorders can occur at any time during treatment. Monitor patients for changes in thyroid function (at the start of treatment, periodically during treatment, and as indicated based on clinical evaluation) and for clinical signs and symptoms of thyroid disorders.

- Grade 2 hyperthyroidism events (and Grade 2-4 hypothyroidism):
 - In hyperthyroidism, non-selective beta-blockers (e.g. propranolol) are suggested as initial therapy.
 - In hypothyroidism, thyroid hormone replacement therapy, with levothyroxine or liothyroinine, is indicated per standard of care.
- **Grade 3-4** hyperthyroidism, treat with an initial dose of IV corticosteroid followed by oral corticosteroids. When symptoms improve to Grade 1 or less, steroid taper should be started and continued over no less than 4 weeks. Replacement of appropriate hormones may be required as the steroid dose is tapered.

Hepatic:

- For **Grade 2** events, monitor liver function tests more frequently until returned to baseline values (consider weekly).
 - Treat with IV or oral corticosteroids
- For Grade 3-4 events, treat with intravenous corticosteroids for 24 to 48 hours.
- When symptoms improve to Grade 1 or less, a steroid taper should be started and continued over no less than 4 weeks.

Renal Failure or Nephritis:

- For Grade 2 events, treat with corticosteroids.
- For Grade 3-4 events, treat with systemic corticosteroids.
- When symptoms improve to Grade 1 or less, steroid taper should be started and continued over no less than 4 weeks.

33

4.5.1 Management of Infusion Reactions:

Signs and symptoms usually develop during or shortly after drug infusion and generally resolve completely within 24 hours of completion of infusion.

Table 4 below shows treatment guidelines for subjects who experience an infusion reaction associated with administration of pembrolizumab (MK-3475).

Table 4.3 Pembrolizumab Infusion Reaction Treatment Guidelines

NCI CTCAE Grade	Treatment	Premedication at subsequent dosing
Grade 1 Mild reaction; infusion interruption not indicated; intervention not indicated	Increase monitoring of vital signs as medically indicated until the subject is deemed medically stable in the opinion of the investigator.	None
Grade 2 Requires infusion interruption but responds promptly to symptomatic treatment (e.g., antihistamines, NSAIDS, narcotics, IV fluids); prophylactic medications indicated for < =24 hrs	Stop Infusion and monitor symptoms. Additional appropriate medical therapy may include but is not limited to: IV fluids Antihistamines NSAIDS Acetaminophen Narcotics Increase monitoring of vital signs as medically indicated until the subject is deemed medically stable in the opinion of the investigator. If symptoms resolve within one hour of stopping drug infusion, the infusion may be restarted at 50% of the original infusion rate (e.g., from 100 mL/hr to 50 mL/hr). Otherwise dosing will be held until symptoms resolve and the subject should be premedicated for the next scheduled dose. Subjects who develop Grade 2 toxicity despite adequate premedication should be permanently discontinued from further trial treatment administration.	Subject may be premedicated 1.5h (± 30 minutes) prior to infusion of pembrolizumab (MK-3475) with: Diphenhydramine 50 mg po (or equivalent dose of antihistamine). Acetaminophen 500-1000 mg po (or equivalent dose of antipyretic).
Grades 3 or 4 Grade 3: Prolonged (i.e., not rapidly responsive to symptomatic medication and/or brief interruption of infusion); recurrence of symptoms following initial improvement; hospitalization indicated for other clinical sequelae (e.g., renal impairment, pulmonary infiltrates) Grade 4: Life-threatening; pressor or 33rticarial support indicated	Stop Infusion. Additional appropriate medical therapy may include but is not limited to: IV fluids Antihistamines NSAIDS Acetaminophen Narcotics Oxygen Pressors Corticosteroids Epinephrine Increase monitoring of vital signs as medically indicated until the subject is deemed medically stable in the opinion of the investigator. Hospitalization may be indicated. Subject is permanently discontinued from further trial treatment administration.	No subsequent dosing

Amendment 6: March 29th, 2019

Initial Version date: March 10th, 2017

4.5.2 **Management of Cardiac Toxicities**

During treatment with pembrolizumab, patients will be closely monitored for cardiac toxicities. For patients with evidence of congestive heart failure. myocardial infarction, cardiomyopathy, or myositis, cardiac evaluation should take place including lab tests and cardiology consultations as clinically indicated including ECG, CPK, troponin, and ECHO.

Pembrolizumab dosing should be modified according to Table 4.5.

Table 4.4 – Management of Cardiac Toxicities			
Cardiac *	Management/Next Dose for Pembrolizumab Cardiac Toxicities		
≤ Grade 1	Hold dose pending evaluation and observation.** Evaluate for signs and symptoms of CHF, ischemia, arrhythmia or myositis. Obtain history EKG, CK (for concomitant myositis), CK-MB. Repeat troponin, CK and EKG 2-3 days. If troponin and labs normalize may resume therapy. If labs worsen or symptoms develop then treat as below. Hold pending evaluation		
Grade >2 with suspected myocarditis	Hold dose.** Admit to hospital. Cardiology consult. Rule out MI and other causes of cardiac disease. Cardiac Monitoring. Cardiac Echo. Consider cardiac MRI and cardiac biopsy. Initiate high dose methylprednisolone. If no improvement within 24 hours, add either infliximab, ATG or tacrolimus. Consult algorithm for more details. Resume therapy if there is a return to baseline and myocarditis is excluded or considered unlikely.		
Grade >2 with confirmed myocarditis	Off protocol therapy. Admit to CCU (consider transfer to nearest Cardiac Transplant Unit). Treat as above. Consider high dose methylprednisolone Add ATG or tacrolimus if no improvement. Off treatment.		

*Including CHF, LV systolic dysfunction, Myocarditis, CPK, and troponin **Patients with evidence of myositis without myocarditis may be treated according as "other event"

Note: The optimal treatment regimen for immune mediated myocarditis has not been established. Since this toxicity has caused patient deaths, an aggressive approach is recommended.

4.5.3 **Diet/Activity/Contraception/Other Considerations**

Subjects should maintain a normal diet unless modifications are required to manage an AE such as diarrhea, nausea or vomiting.

Pembrolizumab may have adverse effects on a fetus in utero. Furthermore, it is not known if pembrolizumab has transient adverse effects on the composition of sperm. For this trial, male subjects will be considered to be of non-reproductive potential if they have azoospermia (whether due to having had a vasectomy or due to an underlying medical condition). Female subjects will be considered of non-reproductive potential if they are either:

> (1) post-menopausal (defined as at least 12 months with no menses without

Initial Version date: March 10th, 2017 34

Amendment 6: March 29th, 2019

an alternative medical cause; in women < 45 years of age a high follicle stimulating hormone (FSH) level in the postmenopausal range may be used to confirm a post-menopausal state in women not using hormonal contraception or hormonal replacement therapy. In the absence of 12 months of amenorrhea, a single FSH measurement is insufficient.); OR

- (2) have had a hysterectomy and/or bilateral oophorectomy, bilateral salpingectomy or bilateral tubal ligation/occlusion, at least 6 weeks prior to screening; OR
- (3) has a congenital or acquired condition that prevents childbearing.

Female and male subjects of reproductive potential must agree to avoid becoming pregnant or impregnating a partner, respectively, while receiving study drug and for 120 days after the last dose of study drug by complying with one of the following:

- practice abstinence[†] from heterosexual activity;
 OR
- (2) use (or have their partner use) acceptable contraception during heterosexual activity.

Acceptable methods of contraception are[‡]:

- Single method (one of the following is acceptable):
 - intrauterine device (IUD)
 - vasectomy of a female subject's male partner
 - contraceptive rod implanted into the skin
- Combination method (requires use of two of the following):
 - diaphragm with spermicide (cannot be used in conjunction with cervical cap/spermicide)
 - cervical cap with spermicide (nulliparous women only)
 - contraceptive sponge (nulliparous women only)
 - male condom or female condom (cannot be used together)
 - hormonal contraceptive: oral contraceptive pill (estrogen/progestin pill or progestin-only pill), contraceptive skin patch, vaginal contraceptive ring, or subcutaneous contraceptive injection

†Abstinence (relative to heterosexual activity) can be used as the sole method of contraception if it is consistently employed as the subject's preferred and usual lifestyle and if considered acceptable by local regulatory agencies and ERCs/IRBs. Periodic abstinence (e.g., calendar, ovulation, 35rticar-thermal, post-ovulation methods, etc.) and withdrawal are not acceptable methods of contraception.

‡If a contraceptive method listed above is restricted by local regulations/guidelines, then it does not qualify as an acceptable method of contraception for subjects participating at sites in this country/region.

Subjects should be informed that taking the study medication may involve unknown risks to the fetus (unborn baby) if pregnancy were to occur during the study. In order to participate in the study subjects of childbearing potential must adhere to the contraception requirement (described above)

from the day of study medication initiation (or 14 days prior to the initiation of study medication for oral contraception) throughout the study period up to 120 days after the last dose of trial therapy. If there is any question that a subject of childbearing potential will not reliably comply with the requirements for contraception, that subject should not be entered into the study.

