4.3.1 Pembrolizumab Dose Modifications

Adverse events (both non-serious and serious) associated with pembrolizumab exposure may represent an immunologic etiology. These adverse events may occur shortly after the first dose or several months after the last dose of treatment. Pembrolizumab must be withheld for drug-related toxicities and severe or life-threatening AEs as per table 4.1 below. See Section 4.5.3 for supportive care guidelines, including use of corticosteroids.

Initial Version date: March 10th, 2017

Amendment 6: March 20th, 2010

Amendment 6: March 29th, 2019

Table 4.1: Dose Modification Guidelines for Pembrolizumab-Related Adverse Events

General instructions:

- Corticosteroid taper should be initiated upon AE improving to Grade 1 or less and continue to taper over at least 4
 weeks.
- 2. For situations where pembrolizumab has been withheld, pembrolizumab can be resumed after AE has been reduced to Grade 1 or 0 and corticosteroid has been tapered. Pembrolizumab should be permanently discontinued if AE does not resolve within 12 weeks of last dose or corticosteroids cannot be reduced to ≤10 mg prednisone or equivalent per day within 12 weeks.
- 3. For severe and life-threatening irAEs, IV corticosteroid should be initiated first followed by oral steroid. Other immunosuppressive treatment should be initiated if irAEs cannot be controlled by corticosteroids.
- 4. For signs or symptoms of Stevens-Johnson Syndrome (SJS) or Toxic Epidermal Necrolysis (TEN), withhold pembrolizumab and refer the patient for specialized care for assessment and treatment.

pembrolizumab and refer the patient for specialized care for assessment and treatment.				
Immune-related AEs	Toxicity grade or conditions (CTCAEv4.03)	Action taken to pembro	irAE management with corticosteroid and/or other therapies	Monitor and follow-up
Pneumonitis	Grade 3 or 4, or recurrent Grade 2	Withhold Permanently discontinue	Administer corticosteroids (initial dose of 1-2 mg/kg prednisone or equivalent) followed by taper	Monitor participants for signs and symptoms of pneumonitis Evaluate participants with suspected pneumonitis with radiographic imaging and initiate corticosteroid treatment Add prophylactic antibiotics for opportunistic infections

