Myocarditis	Grade 1 or 2	Withhold	Based on severity of AE administer corticosteroids	Ensure adequate evaluation to confirm etiology and/or exclude other causes	
	Grade 3 or 4	Permanently discontinue		other causes	
All other immune- related AEs	Intolerable/ persistent Grade 2	Withhold	Based on type and severity of AE administer corticosteroids	Ensure adequate evaluation to confirm etiology and/or exclude other causes	
	Grade 3	Withhold or discontinue based on the type of event. Events that require discontinuatio n include and not limited to: Gullain-Barre Syndrome, encephalitis			
	Grade 4 or recurrent Grade 3	Permanently discontinue			

^{1.} Withhold or permanently discontinue pembrolizumab is at the discretion of the investigator or treating physician.

NOTE:

For participants with Grade 3 or 4 immune-related endocrinopathy where withhold of pembrolizumab is required, pembrolizumab may be resumed when AE resolves to \leq Grade 2 and is controlled with hormonal replacement therapy or achieved metabolic control (in case of T1DM).

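### Tables 4.1 and 4.4 both direct pembrolizumab dosing for myocarditis, with different restart conditions and a defective Grade 2 rule, and nothing says which table prevails

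*Combined protocol and SAP*

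**What the plan says.** Section 4.3.1 makes Table 4.1 binding for withholding pembrolizumab, and Section 4.3.2 calls the pembrolizumab modifications mandatory (while citing Table 4.2, the AVD table, as their location). The Myocarditis row of Table 4.1 withholds the drug at Grade 1 or 2 and stops it permanently at Grade 3 or 4. Its steroid instruction is "Based on severity of AE administer corticosteroids". Restart follows general instruction 2 of that table: "pembrolizumab can be resumed after AE has been reduced to Grade 1 or 0 and corticosteroid has been tapered". The same instruction ends pembrolizumab for good if the event has not resolved within 12 weeks of the last dose, or if steroids cannot be brought down to 10 mg prednisone-equivalent a day within 12 weeks.

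Section 4.5.2 covers cardiac toxicities separately and sends dosing to Table 4.5. The numbered tables in Section 4 run from 4.1 to 4.4, and the one that follows is Table 4.4. Its footnote gives the scope: "Including CHF, LV systolic dysfunction, Myocarditis, CPK, and troponin". It has three rows:

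- Grade 1 or lower: hold and evaluate. "If troponin and labs normalize may resume therapy"; otherwise, "If labs worsen or symptoms develop then treat as below".
- "Grade >2 with suspected myocarditis": hold, admit and treat. "Resume therapy if there is a return to baseline and myocarditis is excluded or considered unlikely".
- The same grade with confirmed myocarditis: off treatment.

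Section 10.3.2 defines unacceptable toxicity, the event counted for continuous toxicity monitoring, as a toxicity requiring discontinuation under Table 4.1. Table 4.4 is not mentioned there.

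**The concern.** Two tables give dosing instructions for the same event, and no sentence ranks them or makes one an exception to the other. The Myocarditis row of Table 4.1 does not refer to Table 4.4, and the pointer in Section 4.5.2 leads to a table number that is not there. Sites that open different pages could restart pembrolizumab on different evidence.

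The event is one where re-exposure matters. The note under Table 4.4 says: "Since this toxicity has caused patient deaths, an aggressive approach is recommended". Every patient is planned to receive three induction doses, and selected patients aged 60 or over may receive 14 or 32 more after a doxorubicin-containing regimen. A secondary question is whether a stop made under Table 4.4 would enter the formal toxicity count.

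**Working it through.** The check is mainly textual. The inputs are general instruction 2 and the Myocarditis row of Table 4.1, the three rows and footnote of Table 4.4, and the event definition in Section 10.3.2.

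**Grade by grade**

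| Myocarditis | Table 4.1 | Table 4.4 | Agreement |
|---|---|---|---|
| Grade 1 | Withhold; restart at Grade 1 or 0 with steroid tapered; 12-week limit | Hold; restart when troponin and labs are normal; no taper or 12-week condition | Agree on holding, differ on restart |
| Grade 2, sign is >2 | Withhold, resumable | No row | Gap in Table 4.4 |
| Grade 2 confirmed, sign is ≥2 | Withhold, resumable | Off treatment | Direct conflict |
| Grade 3-4 confirmed | Permanent stop | Off treatment | Agree |

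**Grade 1.** The grade part of Table 4.1's restart test is met from the outset by an event that was never above Grade 1. What remains is the taper, and steroid use depends on severity, so a mild event may have no steroid to taper. Table 4.4 asks for something Table 4.1 does not (normal troponin and labs) and omits what Table 4.1 does ask for (taper, 12 weeks). Neither rule contains the other.

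**Grade 2.** Suppose the sign is >2. Table 4.1 then covers 4 of 4 grades and Table 4.4 covers 3 of 4. The escalation step in its first row has no target for a case that worsens to Grade 2, and only Table 4.1 gives an instruction. Suppose instead that ≥2 was meant. The gap closes, but confirmed Grade 2 myocarditis then ends treatment under one table and may be resumed under the other. The text does not settle the sign: the ≤ in the first row of Table 4.4 is intact, but comparison signs are missing from the text of Appendix C. The two Grade 2 defects exclude each other, and one of them is present whichever sign is right.

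**Toxicity monitoring (Section 10.3.2).** The printed boundary is 4, 6, 8, 9, 11 and 12 events at 5, 10, 15, 20, 25 and 30 patients. It is the smallest b with P(X ≥ b) at or below a pointwise level, where X is binomial with rate 20%. A level of 0.017, which rounds to the stated 2%, reproduces all six values. For example, at 5 patients P(X ≥ 4) = 0.0067 and P(X ≥ 3) = 0.0579, so b = 4. At 15 patients P(X ≥ 8) = 0.0042 and P(X ≥ 7) = 0.0181, so b = 8. Correcting the tables changes none of these values. The only link is conditional: if ≥2 was meant, a confirmed Grade 2 myocarditis stopped under Table 4.4 would not by itself count, because Table 4.1 does not require that stop. It would count only if Table 4.1's 12-week condition also applied.

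**The case against.** The best defence is that a specific table ordinarily overrides a general one. Section 4.5.2 directs cardiac dosing to its own table, so a reader would follow Table 4.4. Both restart rules are also permissive, and a careful site can satisfy both by waiting for normal labs and a finished taper. Table 4.1 itself asks for adequate evaluation of the cause. This has force, and it limits the practical harm. It does not remove the point: the general table is the one described as binding, Section 4.5 introduces its own measures as suggestions, and nothing tells the site to satisfy both rules.

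A second defence is that the missing Grade 2 row may be only a lost underline. That may be so, but the ≥2 reading replaces the gap with a direct conflict.

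Three stronger readings are tempting and are not supported:

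- A reader might infer that restart with residual Grade 1 after a Grade 2 event depends on which table is followed. That needs the first row of Table 4.4 to cover a Grade 2 event that has come down, and the table does not say so.
- A reader might count the restart condition in the suspected-myocarditis row as a further competing rule. It applies only once myocarditis has been excluded or judged unlikely, so it does not compete with Table 4.1's Myocarditis row.
- A reader might infer that toxicity monitoring is materially weakened. The link holds only under ≥2. All SAEs go to the DSMC (Section 7.3.3), and adverse events leading to withdrawal are listed (Section 10.3.2). Such a case could miss one formal count but would not go unseen.

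**Conclusion.** The point holds as an internal inconsistency affecting dosing safety, of minor-to-moderate severity. Three things stand whichever sign was intended: the two tables have no stated order of precedence, the pointer in Section 4.5.2 is wrong, and the Grade 1 restart conditions differ. Grade 2 is also defective on either reading, as a gap under >2 or as a stop-versus-hold conflict under ≥2. Only the ≥2 reading touches the event count in Section 10.3.2.

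The tables agree on holding at Grade 1 and on stopping confirmed Grade 3-4 myocarditis. The primary endpoint, sample size, power and alpha are unaffected. The documents give no myocarditis rate; I assume few events among up to 30 patients, so the importance lies in the seriousness of each case and not in the number.

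**What to change.** In the next amendment:

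1. Correct the pointer in Section 4.5.2 to Table 4.4, and the one in Section 4.3.2 to Table 4.1.
2. State that Table 4.4 governs cardiac events, myocarditis included, and have the Myocarditis row of Table 4.1 refer to it.
3. Make Grade 2 explicit in Table 4.4 for both suspected and confirmed myocarditis. The sponsor should confirm whether confirmed Grade 2 is a permanent stop; until then, Table 4.1's withhold stands.
4. For restart from Grade 1 or lower, require normalized troponin and labs and completed taper of any corticosteroid, and keep Table 4.1's 12-week limit.
5. In Section 10.3.2, count pembrolizumab discontinuations required by either table.

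The cost is wording in two tables, one definition and two cross-references, with no new procedures or patients. The downside is that a few patients may be held longer before restarting.
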